**TABLE D: SCHEDULE OF ASSESSMENTS: DOSING, SUA, AND URICASE ACTIVITY DURING THE DOUBLE-BLIND EXTENSION PHASE**

Assessments Day Timepoint	Treatment Periods: 7, 8, 9, 10, and 11				Treatment Period 12					
	D0 				D0 				D21 	
	0h	~1.5h	~3.5h	~4.5h		0h	~1.5h	~3.5	~4.5h	
Premedicate: Infusion Reaction	X 					X				
Blood Sample Uricase Activity	X 			X 	X	X 			X 	X
Blood Sample: sUA	X 			X 	X	X 			X 	X
Study Drug Infusion (Component 1) 	X-----X 					X-----X 				
Study Drug Infusion (Component 2) 		X  -----X				X  -----X				

[figure not shown]
1. Study drug dosing to occur 28 days from the previous dose with a window of -4 days to +3 day of the intended dosing day.
2. Only on Treatment Period 7 Day 0: Treatment Period 6 Day 28 assessment will be used for Treatment Period 7 Day 0 pre-dose assessment. Do not repeat sample collection on Treatment Period 7 Day 0.
3. Assessments at this visit are permitted to be performed remotely (inclusive of collecting applicable lab draws and assessments per protocol visit windows).
4. Treatment Period 12 only.
5. Premedication to minimize potential infusion reactions: oral antihistamines at 12 ( $\pm$  2) hours and 2 ( $\pm$  1) hours and IV steroids at 1 ( $\pm$  0.5) hours prior to study drug.
6. Obtain sample prior to study drug infusion.
7. Obtain sample 1 hour (+15/-0 min) after completion of infusion of Component 2.
8. Component 1 will be SEL-110.36 at 0.1 mg/kg for patients randomized to treatment with SEL-212A and SEL-110.36 at 0.15 mg/kg for patients randomized to SEL-212B or will be placebo for patients randomized to placebo.
9. Before starting infusion with Component 2, a period of up to approximately 30 minutes is permitted after completion of infusion of Component 1.
10. Component 2 will be SEL037 for patients randomized to treatment with either SEL212A or to SEL212B or will be placebo for patients randomized to placebo.

This document is confidential.

**TABLE E: DOSING, SERUM URIC ACID, AND URICASE ACTIVITY ASSESSMENT SCHEDULE (TREATMENT PERIODS 1, 2, 3, 4, 5, AND 7, 8, 9, 10, 11)**

[figure not shown]

**TABLE F: DOSING, SERUM URIC ACID, AND URICASE ACTIVITY ASSESSMENT SCHEDULE (TREATMENT PERIOD 6)**

This document is confidential.

**TABLE G: DOSING, SERUM URIC ACID, AND URICASE ACTIVITY ASSESSMENT SCHEDULE  
(TREATMENT PERIOD 12)**

This document is confidential.

## **4. Endpoints**

The main evaluation and confirmatory analysis of efficacy is performed at TP6. The below defined endpoints in 4.1. to 4.3 present the confirmatory and exploratory efficacy analysis of this double-blind treatment period. However, efficacy will be assessed in the double-blind extension period, also, and descriptive summaries of most of the endpoints (but considering TPs 7 to 12 instead of TPs 1 to 6) listed below will be provided. The exploratory efficacy endpoints for the extension period are listed in Section 4.4.

### **4.1. Primary Efficacy Endpoint**

Each of the two active treatment groups, SEL-212A and SEL-212B, are compared to placebo with regards to the following primary endpoint:

- The percentage of patients who achieve and maintain reduction of sUA < 6 mg/dL for at least 80% of the time during Treatment Period 6 by Day 28

### **4.2. Secondary Efficacy Endpoints**

#### Key Secondary Endpoints:

Each of the two active treatment groups, SEL-212A and SEL-212B, are compared to placebo with regards to the following key secondary endpoints:

- Reduction of mean sUA as computed by subtracting the Baseline sUA level from the mean sUA during Treatment Period 6
- Percent reduction of mean sUA as computed by subtracting the Baseline sUA level from the mean sUA during Treatment Period 6
- The change from Baseline to Day 28 of Treatment Period 6 in the physical summary score of the Short Form Health Survey (SF-36)
- In patients with tophi at Baseline, the percentage of patients with at least PR (as best response) in overall tophus response evaluation until Day 28 of Treatment Period 6
- The percentage of patients who achieve and maintain reduction of sUA < 6 mg/dL for at least 80% of the time during Treatment Period 6 by Day 28, in the subset of patients with tophi at baseline
- The change from Baseline to Day 28 of Treatment Period 6 in number of tender joints
- The change from Baseline to Day 28 of TP6 in the total score of the Health Assessment Questionnaire (HAQ-DI)
- Gout flare incidence during Treatment Periods 1-6
- Gout flare incidence during Treatment Periods 1-3

#### Additional Secondary Endpoints:

Each of the two active treatment groups, SEL-212A and SEL-212B, are compared to placebo with regards to the following additional secondary efficacy endpoints:

- Percentage of patients who achieve and maintain reduction of sUA < 6 mg/dL for 100% of the time during Treatment Period 6
- Number of pre-dose sUA values < 6 mg/dL during Treatment Periods 2-6 for each patient

This document is confidential.

- Pre-treatment anti-pegadricase and anti-uricase antibody formation and levels in each treatment period in the SEL-212 active treatment arms during Treatment Periods 1-6
- Percentage of patients with development of new tophi in the subgroups of tophaceous patients and in non tophaceous patients at Baseline during Treatment Periods 1-6
- In patients with tophi at Baseline, the percentage of patients with at least PR (as best response) in overall tophus response evaluation until Day 0 of Treatment Period 4
- Change from baseline to Day 28 of TP6 in subscales of Health Assessment Questionnaire (HAQ-DI), in Provider Global Assessment of Disease Activity, and in subscales of Short Form Health Survey (SF-36)
- Percentage of patients with at least one gout flare in Treatment Periods 1-3
- Percentage of patients with at least one gout flare in Treatment Periods 1-6
- Change from Baseline to Day 28 of Treatment Period 6 in number of swollen joints
- Length of time patients are anti-uricase antibody free or before induction of anti-uricase antibody levels above baseline in patients receiving SEL-212 during Treatment Periods 1-6
- Length of time patients are anti-pegadricase antibody free or before induction of anti-pegadricase antibody levels above baseline in patients receiving SEL-212 during Treatment Periods 1-6

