- Reduction of mean sUA as computed by subtracting the Baseline sUA level from the mean sUA (area under the sUA time curve) during Treatment Period 6
- Percent reduction of mean sUA as computed by subtracting the Baseline sUA level from the mean sUA (area under the sUA time curve) during Treatment Period 6
- The change from Baseline to Day 28 of Treatment Period 6 in the physical summary score of the Short Form Health Survey (SF-36)
- In patients with tophi at Baseline, the percentage of patients with at least partial response (PR) (as best response) in overall tophus response evaluation until Day 28 of Treatment Period 6
- The percentage of patients who achieve and maintain reduction of sUA < 6 mg/dL for at least 80% of the time during Treatment Period 6 in subset of patients with tophi at baseline
- The change from Baseline to Day 28 of Treatment Period 6 in the number of tender joints

- The change from Baseline to Day 28 of Treatment Period 6 in the total score of the Health Assessment Questionnaire (HAQ-DI)
- Gout flare incidence during Treatment Periods 1-6
- Gout flare incidence during Treatment Periods 1-3

Additional Secondary Efficacy Endpoints:

Each of the two active treatment groups, SEL-212A and SEL-212B, are compared to placebo with regards to the following additional secondary efficacy endpoints:

- The percentage of patients who achieve and maintain reduction of sUA < 6 mg/dL for 100% of the time during Treatment Period 6
- Percentage of pre-dose sUA values < 6 mg/dL during Treatment Periods 2-6 for each patient
- Pre-treatment anti-pegadricase and anti-uricase antibody formation and levels in each treatment period in the SEL-212 active treatment arms during Treatment Periods 1-6
- The percentage of patients with development of new tophi in the subgroups of tophaceous patients and in non-topheaceous patients at Baseline during Treatment Periods 1-6
- In patients with tophi at Baseline, the percentage of patients with at least PR (as best response) in overall tophus response evaluation until Day 0 of Treatment Period 4
- Change from Baseline to Day 28 of Treatment Period 6 in subscales of Health Assessment Questionnaire (HAQ-DI), in Provider Global Assessment of Disease Activity, and in subscales of Short Form Health Survey (SF-36)
- The percentage of patients with at least 1 gout flare during Treatment Periods 1-3
- The percentage of patients with at least 1 gout flare during Treatment Periods 1-6

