6.2.2.2 Additional Secondary Efficacy Endpoints for Double-Blind Treatment Phase

Each of the two active treatment groups, SEL-212A and SEL-212B, are compared to placebo with regards to the following additional secondary efficacy endpoints:

- The percentage of patients who achieve and maintain reduction of sUA < 6 mg/dL for 100% of the time during Treatment Period 6

- Percentage of pre-dose sUA values \leq 6 mg/dL during Treatment Periods 2-6 for each patient
- Pre-treatment anti-pegadricase and anti-uricase antibody formation and levels in each treatment period in the SEL-212 active treatment arms during Treatment Periods 1-6
- The percentage of patients with development of new tophi in the subgroups of tophaceous patients and in non-tophaceous patients at Baseline during Treatment Periods 1-6
- In patients with tophi at Baseline, the percentage of patients with at least PR (as best response) in overall tophus response evaluation until Day 0 of Treatment Period 4
- Change from Baseline to Day 28 of Treatment Period 6 in the subscales of Health Assessment Questionnaire (HAQ-DI), in Provider Global Assessment of Disease Activity, and in subscales of Short Form Health Survey (SF-36)
- The percentage of patients with at least 1 gout flare during Treatment Periods 1-3
- The percentage of patients with at least 1 gout flare during Treatment Periods 1-6
- Change from baseline to Treatment Period 6 in number of swollen joints
- Length of time patients are anti-uricase antibody free or before induction of anti-uricase antibody levels above baseline in patients receiving SEL-212
- Length of time patients are anti-pegadricase antibody free or before induction of anti-pegadricase antibody levels above baseline in patients receiving SEL-212

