13.4.3 Further Secondary Efficacy Endpoints and Analyses in the Double-Blind Treatment Phase

Additional secondary efficacy endpoints will be summarized by treatment group using descriptive statistics on the ITT population and will be compared between each SEL-212 treatment group and placebo using MH considering the randomization stratum tophus presence (yes/no) in case of binary endpoints or using, or using continuity corrected Chi-square test in case of binary endpoints within subgroups with/without tophi at baseline. In case of continuous or numerical endpoints treatment groups will be compared by ANCOVA, or MMRM as appropriate. All tests – except the tests within subgroups of tophus yes/no at Baseline - will adjust for the randomization stratum and will present exploratory p-values of two-sided tests. In addition, 95% confidence intervals for treatment differences between each SEL-212 treatment group and placebo will be computed. Details will be provided in the SAP.

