### **9.3.3. Additional Secondary Efficacy Endpoints and Analyses**

- Percentage of patients who achieve and maintain reduction of sUA < 6 mg/dL for 100% of the time during TP6:

A frequency table of number and percentage of patients who achieve and maintain reduction of sUA < 6 mg/dL for 100% of the time during TP6 will be provided on the ITT population. Each SEL-212 treatment group will be compared versus placebo using the MH estimate and test for common risk difference considering the randomization stratum of tophus presence (yes/no) on the ITT population. In addition, 95% confidence intervals for treatment differences between each SEL-212 treatment group and placebo will be computed.

- Number with pre-dose sUA values < 6 mg/dL during TPs 2-6 for each patient:

A summary table of the mean number of TPs with pre-dose sUA values < 6 mg/dL during TP2 to TP6 will be provided by treatment group on the ITT population. Each SEL-212 treatment group will be compared versus placebo using ANCOVA model with the number of pre-dose values < 6 mg/dL during TPs 2-6 for each patient as dependent variable and treatment group as independent fixed effect variable. 95% confidence intervals for treatment differences between each SEL-212 treatment group and placebo will be presented.

- Anti-pegadricase and anti-uricase antibody formation and levels, pre-treatment for each treatment period in the SEL-212 active treatment arms during Treatment Periods 1-6:

Summary table of pre-treatment values of each variable will be provided by treatment period and by SEL-212 treatment group on the ITT population.

A descriptive summary table of D21 anti-pegadricase and anti-uricase antibody titers, D21 uricase activity values and D21 SUA values at each treatment period, stratified by treatment arm and whether or not the D21 SUA was above or less than or equal to the stopping rule level for that TP (i.e.  $\leq 1$  mg/dL in TP1 and  $\leq 6$  mg/dL in TPs 2-6).

This document is confidential.

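### SAP 9.3.3 leaves the tophus stratum out of the pre-dose sUA test and replaces the protocol's percentage with a count, and declares neither change

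*SAP*

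**What the plan says.** **Endpoint.** The protocol synopsis gives "Percentage of pre-dose sUA values < 6 mg/dL during Treatment Periods 2-6 for each patient". Protocol 6.2.2.2 also begins "Percentage of pre-dose sUA values", but prints the threshold as ≤ 6 rather than < 6. SAP 4.2 has instead "Number of pre-dose sUA values < 6 mg/dL during Treatment Periods 2-6 for each patient".

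**Model.** SAP 9.3.3 names an ANCOVA on the ITT set in which the count enters "as dependent variable and treatment group as independent fixed effect variable". It lists no stratum and no covariate.

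**Stratum rule.** Protocol 13.4.3, which governs the additional secondary endpoints, states: "All tests – except the tests within subgroups of tophus yes/no at Baseline - will adjust for the randomization stratum". Randomisation is stratified by tophi only (Protocol 7.3).

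**Missing samples.** SAP 7.3 confines imputation to the primary and key secondary variables. SAP 7.4 lets a value from an unscheduled visit stand in for a missing scheduled one if it falls between the neighbouring scheduled visits.

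**Declaration.** Protocol Section 13 says that modifications to planned analyses will be flagged in the final SAP. SAP Section 12 lists one change, the use of ANOVA for gout flares.

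**The concern.** The SAP departs from the protocol in two ways.

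First, the test does not use the factor that the trial randomises by, although the protocol says it should. If tophus status predicts urate control, the between-stratum variation stays in the residual and the standard error is larger than it need be.

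Second, a count has a fixed implicit denominator of five (Treatment Periods 2 to 6). A sample that was never drawn adds nothing, just like a sample at or above 6 mg/dL. The endpoint then mixes urate control with sample availability, and unequal availability between arms would enter the treatment contrast. The protocol's percentage does not carry this arithmetic penalty.

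Because Section 12 mentions neither point, a reader of the results could not tell a deliberate change from an oversight.

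**Working it through.** **Plan figures.** The documents give no effect size, variance or power for this endpoint. The protocol's sample size (32 per arm; 32/0.92 = 34.8, so 35; 3 × 35 = 105; plus 15 = 120) concerns the primary endpoint and is unaffected.

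**1. Does the stratum rule apply?** The only exception in Protocol 13.4.3 is for tests within tophus subgroups. This test uses the whole ITT set, so the rule applies. The other whole-ITT between-arm tests in SAP 9.3.3 follow it: response for 100% of the time and patients with flares by stratified Mantel-Haenszel; the health scores and swollen joints by MMRM with the stratum. This endpoint is the odd one out.

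**2. Cost of leaving out the stratum.** With R² the share of within-arm variance explained by tophus status, the unadjusted standard error is larger by 1/√(1 − R²). The documents do not give R², so these values are assumptions:

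| R² | SE factor |
|---|---|
| 0 | 1.000 |
| 0.02 | 1/√0.98 = 1.010 |
| 0.05 | 1/√0.95 = 1.026 |
| 0.10 | 1/√0.90 = 1.054 |

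A simulation checked this: 4,000 runs, 40 v 40 patients, 60% with tophi, a linear model on the count, complete data, two-sided 5%. The tophus difference in control rate is assumed.

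| Tophus difference | Type I error, with → without stratum | Power, with → without stratum |
|---|---|---|
| 0 points | 4.6% → 4.7% | 99.4% → 99.4% |
| 20 points | 4.8% → 4.2% | 97.6% → 97.3% |
| 40 points | 4.7% → 2.8% | 89.0% → 86.1% |

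Compare within rows only; the average control rate also shifts between rows. Without the stratum the test is not anti-conservative. It becomes conservative and loses some power when tophus status matters.

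**3. Count against percentage.** With all five samples, percentage = (count/5) × 100 = 20 × count, so the two give the same test. They part only when samples are missing. For a patient whose every available value is below 6:

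| Samples available | Percentage of available | Count | Count rescaled (count/5 × 100) |
|---|---|---|---|
| 5 | 100 | 5 | 100 |
| 4 | 100 | 4 | 80 |
| 3 | 100 | 3 | 60 |

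In the same simulation (20-point tophus difference, stratum included), with assumed rates of missed and unreplaced samples:

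| Missed, active / placebo | Difference, count rescaled | Difference, percentage |
|---|---|---|
| 10% / 10% | 28.7 points | 31.8 points |
| 20% / 10% | 24.1 points | 31.8 points |

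**The case against.** Much can be said for the SAP, and most of it limits the size of the point.

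- *The count is not foreign to the protocol.* Protocol 6.2.4 uses a number of pre-dose values for the extension phase. That is true, but for Treatment Periods 2–6 both protocol lists say percentage.
- *Missing samples should be few.* Patients withdrawn from study drug keep their visits to the end of Treatment Period 12 (Protocol 7.4.1.1). Appendix B waives only their post-dose samples, and SAP 7.4 allows replacement. This stands. A reader might infer that every missed sample is scored as uncontrolled; the penalty reaches only samples that are missed and not replaced. The documents give no missingness by arm for this endpoint.
- *The error is mostly conservative.* If placebo values are rarely below 6, missed samples chiefly lower the active score. This is reasonable, and the simulation agrees.
- *The percentage has its own weakness.* Someone controlled at two visits who then leaves scores 100, and a patient with no values has no score. This is right, so the percentage needs a missing-data rule.
- *Protocol 13.4.3 leaves details to the SAP.* That covers the choice of ANCOVA or MMRM. It does not cover the stratum, which the same section fixes.
- *The threshold conflict may be trivial.* The ≤ 6 is internal to the protocol and could be an artefact of text extraction. SAP Section 12 would not be expected to list it.

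**Conclusion.** The point holds as a small consistency defect. The SAP model omits a stratum that the protocol requires, the SAP endpoint is a count where the protocol has a percentage, and Section 12 declares neither.

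The precision at stake is nil if tophus status is not prognostic, and about 1–5% of the standard error if it explains 2–10% of the variance. That range is assumed. The effect of the count depends wholly on unreplaced missing samples: 20 points on a 0–100 scale for each one in an otherwise fully controlled patient.

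A reader might infer three stronger things that the documents do not support:

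- *That the SAP also breaks the protocol by leaving out baseline sUA.* No section requires it for this endpoint. A gain of 3–8% (√(1 − R²) = 0.975 to 0.922 for R² of 0.05 to 0.15) would assume a combined contribution of stratum and baseline, so it cannot be charged to the protocol departure.
- *That using a count itself loses precision.* With complete data the test is identical.
- *That the trial's conclusions are at risk.* Protocol 13.4.3 makes these p-values exploratory, and the endpoint lies outside the testing hierarchy.

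**What to change.** 1. In SAP 9.3.3, add the tophus randomisation stratum to the model for this endpoint. Baseline sUA may be added as an optional covariate.
2. Restore the protocol's percentage in SAP 4.2 and 9.3.3. State the denominator (for example, available pre-dose values in Treatment Periods 2–6 after the SAP 7.4 substitution) and a rule for patients with few or no available values. Alternatively, keep the count and declare and justify it in SAP Section 12.
3. Reconcile the < 6 mg/dL in the synopsis and SAP with the ≤ 6 mg/dL in Protocol 6.2.2.2.

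The cost is SAP wording and one model line, plus a protocol clarification for the threshold; no new data are needed. The downside is small: a percentage of available values can favour patients who leave while controlled, which is why step 2 asks for the missing-data rule.

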#### **4.3. Exploratory Endpoints for the Double-blind Treatment Phase**

- Levels of uricase activity in patients receiving SEL-212
- Levels of monosodium urate crystal deposits and/or total body monosodium urate crystal deposits (imaging patients only)
- Levels of inflammatory and tolerogenic biomarkers
- Changes in antibody production (anti-uricase and anti-pegadricase) in patients in the SEL-212 groups
- Gout flare incidence during Treatment Periods 4-6
- Gout flare incidence during Treatment Periods 1-3 based on self-reported weekly gout flare diary
- Gout flare incidence during Treatment Periods 1-6 based on self-reported weekly gout flare diary
- Gout flare incidence in the Treatment Periods 4-6 based on self-reported weekly gout flare diary
- Assessment of association between multiomic markers of gout and treatment effect in patients treated with SEL-212
- Immune tolerance related multiomic markers in patients on SEL-212 who developed anti-uricase and anti-pegadricase antibodies vs. those patients on SEL-212 that did not develop anti-uricase and anti-pegadricase antibodies

#### **4.4. Exploratory Endpoints for the Double-blind Extension Phase**

- The change from Baseline to each Treatment Period (7 to 12) in extension phase of sUA level

This document is confidential.

**Statistical Analysis Plan**

Sponsor: Selecta Biosciences

Protocol No.: SEL-212/301

- The change from Baseline to each Treatment Period (7 to 12) in extension phase in number of tender joints and number of swollen joints
- In patients with tophi at Baseline, the percentage of patients with at least PR (as best response) in overall tophus response evaluation in each Treatment Period (7 to 12) in the extension phase
- The change from Baseline to each Treatment Period (7 to 12) in extension phase in the total score and in subscales of the Health Assessment Questionnaire (HAQ-DI)
- The change from Baseline to each TP (7 to 12) in extension phase in the summary score and in subscales of the Short Form Health Survey (SF-36)
- Gout flare incidence in the Treatment Periods 1 to 9 and in the Treatment Periods 1 to 12 and percentage of patients with at least one gout flare in the Treatment Periods 1 to 9 and in the Treatment Periods 1 to 12 in extension phase in the subgroup of patients continued into extension phase
- Number of pre-dose sUA values < 6 mg/dL for each patient stratified by cumulative number of treatment periods 7 to 12 for the subgroup of patients continued into extension phase
- Pre-treatment anti-pegadricase and anti-uricase antibody formation and levels for each treatment period during extension phase in the SEL-212 active treatment arms
- Percentage of patients with development of new tophi in each Treatment Period (7 to 12) in extension phase in the subgroups of tophaceous patients and in non tophaceous patients at study baseline (Day 0 TP1) and at baseline of extension phase (Day 0 TP7)
- Change from baseline to each Treatment Period (7 to 12) in extension phase in Provider Global Assessment of Disease Activity
- Length of time patients are anti-uricase antibody free or before induction of anti-uricase antibody levels above baseline in patients receiving SEL-212 in the subgroup of patients continued into extension phase
- Length of time patients are anti-pegadricase antibody free or before induction of anti-pegadricase antibody levels above baseline in patients receiving SEL-212 during extension phase
- Levels of uricase activity in patients receiving SEL-212 during extension phase
- Levels of monosodium urate crystal deposits and/or total body monosodium urate crystal deposits (imaging patients only) during extension phase
- Levels of inflammatory and tolerogenic biomarkers during extension phase
- Changes in antibody production (anti-uricase and anti-pegadricase) in patients in the SEL-212 groups during extension phase
- Assessment of association between multiomic markers of gout and treatment effect in patients treated with SEL-212 during extension phase
- Immune tolerance related multiomic markers in patients on SEL-212 who developed anti-uricase and anti-pegadricase antibodies vs. those patients on SEL-212 that did not develop anti-uricase and anti-pegadricase antibodies

This document is confidential.

